3.0 Patient Eligibility

3.1 Patient Inclusion Criteria

1. Patient 18 years old or older.
2. English and non-English speaking patients are eligible.
3. Patient post a cord blood transplant (CBT) or haplo-SCT, mismatched unrelated donors (mMUDmatched), unrelated donors (MUDs), matched related donors (MRDs), both PB and marrow sources with documented absolute neutrophil engraftment.
4. Patients with documented engraftment but require G-CSF to treat myelosuppression induced by drugs used to treat or prevent infection are eligible.
5. Karnofsky performance status (KPS) > 60%.
6. Adequate organ function:
 - Pulmonary: Absence of dyspnea or hypoxia (< 90% of saturation by pulse oximetry on room air).
 - Hepatic: Bilirubin <= 1.5 X ULN, AST (SGOT) and /or ALT (SGPT) <= 2.5 X ULN. PT/PTT < 1.5 X ULN.
 - Renal: Calculated Creatinine clearance > 50 mL/min/1.73 m².
7. Diagnosis of acute myeloid leukemia; myelodysplastic syndrome; chronic myeloid leukemia; myelofibrosis or myeloproliferative disease.
8. Patients are allowed to enroll on this study if they are enrolled on another IND trial.

3.2 Patient Exclusion Criteria

1. Pregnant or nursing.
2. History of lymphoid malignancy (including Hodgkin disease, non-Hodgkin lymphoma, Acute Lymphoblastic Leukemia and Chronic Lymphocytic Leukemia) or acute biphenotypic leukemia.
3. Patients with acute GVHD > grade 2 at any time during the post-transplant course.
4. Ongoing immunosuppressive therapy for the treatment of GVHD. Patients receiving GVHD prophylaxis will be allowed on this study.
5. History of EBV associated lymphoproliferation.
6. Active uncontrolled viral, bacterial or fungal infection.
7. History of autoimmune disease.
8. Receiving systemic corticosteroid therapy at </=5 mg, budesonide is allowed.
9. Uncontrolled hypertension.
10. QTc prolongation (QTc > 470 ms) or prior history of significant arrhythmia or ECG abnormalities.
11. Active drug or alcohol use or dependence that, in the opinion of the investigator, would interfere with adherence to study requirements.
12. Patients with cognitive impairments and/or any past or current psychiatric illness that, in the opinion of the investigator, would interfere with adherence to study requirements or the ability and willingness to give written informed consent.

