7.2 Baseline covariates

Baseline patient covariates to be recorded at enrollment will include the following variables:

Conditioning regimen received
GVHD prophylaxis
Type of donor
Type of graft
Time to engraftment from cell infusion
Donor age
Acute (grades 2 – 4) GVHD
Patient age
Time to neutrophil engraftment
Time to platelet engraftment
Disease (AML or MDS)

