Active treatment period (ATP) is defined from the first injection of CYT107 through 30 days from

the last injection.

Time for Adverse Event (AE) Collection:

Adverse events will be collected from the first injection of CYT107 through 30 days from the last injection. AEs that occur up to 30 days from the last injection of CYT107 will be followed until resolution.

The collection of adverse events will reflect the onset and resolution date and maximum grade. If a patient is taken off study while an event is still ongoing, this will be followed until resolution or the event has stabilized. Pre-existing medical conditions will be recorded only if an exacerbation occurs during the active treatment period. Co-morbid events will not be scored separately.

Adverse Event Reporting:

The Investigator or physician designee is responsible for verifying and providing source documentation for all adverse events, and assigning attribution for each event on all subjects enrolled on this study.

Adverse events will be documented and entered into the electronic case report form (REDCap/CORe). All protocol specific data will be entered into REDCap/CORe.

Events not to be considered adverse events in this study are those related to original disease or expected in the post-allogeneic transplant period.

Isolated changes in laboratory parameters such as electrolyte, magnesium and metabolic imbalances, uric acid changes, elevations of GPT, GOT, LDH and alkaline phosphatase will not be captured.

Concomitant medications

Patients treated on this protocol will require supportive care treatment (concomitant medications). These medications are considered standard of care and have no scientific contribution to the protocol; therefore no data will be captured on various medications needed or their side effects. All concomitant medications will be captured in the medical record.

Causality Assessment.

The principal investigator will be the final arbiter in determining the causality assessment.

List of most common expected adverse events:

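### Exclusion item 8 on systemic corticosteroids is wrong as written: read literally it excludes 5 mg or less and admits higher doses, and it lacks a time unit and reference steroid

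*Combined protocol and SAP*

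**What the plan says.** Item 8 of section 3.2 (Patient Exclusion Criteria) is the only line in the document that sets a corticosteroid dose threshold: "Receiving systemic corticosteroid therapy at </=5 mg, budesonide is allowed". It gives a number and a direction but no time unit, such as per day, and no reference steroid, such as prednisone equivalent.

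The nearest related criterion is item 4 of the same list: "Ongoing immunosuppressive therapy for the treatment of GVHD. Patients receiving GVHD prophylaxis will be allowed on this study". It has two parts, an excluded therapy followed by a permitted one. It sets no steroid dose.

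Two other places bear on steroid use without limiting it. Section 7.2 lists GVHD prophylaxis among the baseline covariates. The concomitant medication paragraph of section 9.0 says that supportive medications are not collected as study data, but adds that "All concomitant medications will be captured in the medical record".

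**The concern.** An eligibility line is applied to every screened patient, so it has to produce the intended decision when followed as written. This one does not. A screener who takes the exclusion list at face value would turn away a patient on a low steroid dose, or record that patient as an eligibility violation, and would find nothing in item 8 to stop a patient on a higher dose. A screener who reads past the wording to the probable intent would decide the other way.

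The missing unit and reference steroid add a second problem. Even when the direction is guessed correctly, the threshold is not fully specified, because a milligram figure for a steroid is definite only once the drug and the period are named.

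What is at stake is correct and consistent eligibility decisions.

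**Working it through.** No arithmetic lies behind this point and the plan states no figure to reproduce. The check is a reading of item 8 in its list, followed by a search for anything elsewhere that would settle its meaning.

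**Step 1: the two readings, by dose band.** The inputs are the wording of item 8, the heading of the list it sits in, and the two-part form of item 4.

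- *Literal reading.* The condition that excludes is receipt of systemic corticosteroid at 5 mg or less. Budesonide is exempt.
- *Inferred reading.* Item 8 follows the form of item 4, with an exclusion first and an allowance second. Systemic corticosteroid is excluded by virtue of the heading, while 5 mg or less, and budesonide, are allowed.

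| Systemic corticosteroid dose | Literal reading | Inferred reading | Wording proposed below |
|---|---|---|---|
| None | not excluded | not excluded | not excluded |
| Above 0, up to 5 mg | excluded | allowed | allowed |
| Above 5 mg | not excluded | excluded | excluded |

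The readings agree only for patients on no systemic steroid. They conflict in both bands where item 8 has work to do. The bands are categories of dose and say nothing about how many patients fall in each.

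**Step 2: which reading is probably meant.** A rule that bars low exposure and admits high exposure has no evident rationale. The budesonide allowance, and the exclusion in item 4 of immunosuppression for GVHD, both fit a rule that tolerates little steroid exposure and bars more. The inferred reading is therefore the likely intent, but the document does not state it.

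**Step 3: whether anything else settles it.**

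- Section 3.1 has no steroid criterion.
- Item 4 of section 3.2 covers immunosuppression only when it is given to treat GVHD. It permits prophylaxis and names no dose.
- Sections 4.0 and 5.1 set no steroid limit.
- The concomitant medication paragraph in section 9.0 sets no steroid limit.

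No other text supplies a direction, a time unit or a reference steroid.

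**Step 4: who could be affected.** A patient on steroids to treat GVHD is excluded by item 4 at any dose, whichever way item 8 is read. Item 6 (uncontrolled infection) and item 7 (autoimmune disease) may remove some further users. What is left is systemic steroid given for other reasons. The document gives no prevalence of such use, so the number cannot be estimated and may be zero. The trial enrols at most 21 patients (section 7.3.1).

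**Step 5: whether an error could be found later.** Steroid use could be checked in the medical record, and a steroid given as GVHD prophylaxis might appear in that baseline covariate. Because concomitant medications are not collected as study data, finding other use would need chart review.

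**The case against.** The strongest reply is that a competent transplant team would know what is meant. On the model of item 4, item 8 can be read as an exclusion with an allowance attached, and the section heading then supplies the exclusion of higher doses. That reading defines all three dose bands and matches the rule proposed here. The trial is small and run by one institution's transplant department, so divergent decisions by different screeners are hypothetical.

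Much of this stands. A reader might infer from the literal wording that item 8 cannot be applied at all, or that no reading excludes doses above 5 mg. The documents do not support either claim, because the inferred reading is available and natural enough. What it does not do is displace the literal wording, which is what the line says, or supply the missing unit and reference steroid.

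A reader might also try to prove a reversed sign from the other limits. In section 3.2, "Patients with acute GVHD > grade 2 at any time during the post-transplant course" and "QTc prolongation (QTc > 470 ms) or prior history of significant arrhythmia or ECG abnormalities" use the greater-than sign for the excluded range, while section 3.1 uses the opposite sign for an acceptable range in "Hepatic: Bilirubin <= 1.5 X ULN, AST (SGOT) and /or ALT (SGPT) <= 2.5 X ULN". The comparison is selective. In the same inclusion item, a less-than sign marks the unacceptable oxygen saturation (below 90%), and greater-than signs mark the acceptable performance status (above 60%) and creatinine clearance (above 50). The signs follow the clinical direction of each variable and show no drafting convention.

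Finally, the missing time unit might tempt a reader to treat 5 mg as a per-dose limit and to compute a higher daily ceiling. Nothing in the documents suggests a per-dose limit, so no such range is offered.

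In the other direction, the tolerance in section 6.0 for variations in protocol requirements does not help the plan. Its examples are off-schedule laboratory tests and missed research samples, and it does not define who may enrol.

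**Conclusion.** Item 8 is wrong as written. Followed literally, it excludes patients on 5 mg or less of systemic corticosteroid and leaves those on more than 5 mg eligible, the reverse of the apparent intent. The likely rule can be inferred, but it competes with the literal one and lacks a time unit and reference steroid.

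The size is small. The effect is confined to steroids given for reasons other than treating GVHD, in an unknown and possibly zero number of patients. A reader might go on to infer a safety hazard, a bias between dose groups, or an effect on the sample size or on the safety rule's operating characteristics. The documents give no basis for any of these, since they report no steroid use and no relation between steroid use and dose assignment.

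That the wording is defective rests on the text alone and is firm. The intended rule, including the per-day unit and prednisone equivalence, is an assumption for the sponsor to confirm. Severity is minor.

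**What to change.** Reword item 8 as: *Receiving systemic corticosteroid therapy at > 5 mg/day prednisone equivalent; doses of 5 mg/day or less and budesonide are allowed.* The sponsor should confirm the direction, the time unit and the reference steroid before the wording is adopted. Item 4 needs no change.

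The cost is a one-line correction to the eligibility criteria in an amendment. It adds no procedures or data collection and leaves the sample size, randomization and within-dose safety rule as they are.

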4.0 Treatment Plan and Study Design

CYT107 will not be administered before Day 60 but could be started as late as Day 180 post-CBT or haplo-SCT.

The active treatment period will be from the first injection of CYT107 and for 30 days after the last injection. The follow-up period will be for three years after the last injection.

Patients will be treated with CYT107 by intramuscular route (I.M.)* post CBT or haplo-SCT (from 60 to 180 days), with 1 of 3 doses below:

- 5 mcg/kg/dose for 3 doses, one week apart
- 10 mcg/kg/dose for 3 doses, one week apart
- 20 mcg/kg/dose for 3 doses, one week apart

Enrollment of the first 3 participants will be staggered by 14 days. Accrual in between cohorts will be halted for 30 days after the last patient in each cohort has received the last dose of CYT107.

* If the patient's platelet count is below 35,000, the product may be administered by subcutaneous route.

All patients will receive foscarnet for the management of CMV infection as per Stem Cell Transplantation and Cellular Therapy Department's standard of care.

Dose modifications

Treatment will be permanently discontinued for patients developing grade 3 or 4 GVHD, secondary graft failure, disease relapse, PTLD, PML, grade 2-4 skin rash, or grade 3-4 non-hematological toxicity attributable to CYT107.

Patients who develop grade 2 non-hematological toxicity attributable to the CYT107 will have the next dose withheld until the toxicity resolves to grade 1. If the toxicity resolves within 2 weeks the drug will be administered at the same dose, however if the toxicity takes more than 2 weeks to resolve the drug will be administered at the next lower level, or permanently discontinued if the patient was already at the lowest level. If the toxicity takes more than 4 weeks to improve to grade 1, the CYT107 will be permanently discontinued

For patients who at study entry have grade 0, 1 or 2 hematological toxicity and develop grade IV hematological toxicity attributable to the CYT107 will have the next dose withheld until the toxicity resolves to grade 2. If the toxicity resolves within 2 weeks the drug will be administered at the same dose, however if the toxicity takes more than 2 weeks to resolve the drug will be administered at the next lower level, or permanently discontinued if the patient was already at the lowest level. If the toxicity takes more than 4 weeks to improve to grade 2, the CYT107 will be permanently discontinued

There are no planned dose modifications for patients who already have grade 3-4 hematological toxicity at study entry

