A flip-top vial is restricted for use by a single patient. Take no more than 0.5 mL into the syringe. The dose to be injected will be divided as necessary into intramuscular injections so that each injection will not exceed 0.5 mL in volume. (Dosing guidelines for ideal body weight make the requirement for multiple injections highly unlikely).

Body Weight (BW) Calculation

If patient is \leq 20% of ideal body weight (IBW), use actual weight.

In obese patients, a corrected weight will be used to calculate the final dose the patient will receive. The corrected dose will be calculated and used if the patient's actual weight give a Body Mass Index (BMI) at the upper limit of normal (i.e. BMI >30).

BMI=weight (Kg)/[height(m)]²

A BMI calculator is provided by www.cdc.gov:

https://www.cdc.gov/healthyweight/assessing/bmi/adult_bmi/english_bmi_calculator/bmi_calculator.html

If BMI >30 proceed with the following steps to determine the adjusted body weight for the dose calculation:

- Determines Ideal weight (1 kg=2.2 lbs):
 - Males: 50 kg + (2.3kg/inch over 5 ft)
 - Females 45.5 kg + (2.3kg/inch over 5 ft)
- Determine Adjusted Body weight:
 - Ideal Weight + 0.25 (actual weight - ideal weight)= Adjusted Body Weight

CYT107 Presentation and Packaging

CYT107 is supplied as a sterile colorless liquid in 2 cc glass vials that are packed individually in cardboard box. Labels are stuck on vial and box.

The labeling is following local and GMP rules. The detailed description of labeling is provided in the Pharmacy Manual.

CYT107 Storage Accountability and Return of Unused Product

Study product will be stored frozen at -25°C to -10°C until used.

The Investigational Pharmacy will maintain complete records of all study products received, stored and subsequently dispensed.

Per MDACC standard, empty, partially used, and expired vials will not be retained. These vials will be discarded immediately upon use in accordance with waste stream policy.

MD Anderson's Investigational Pharmacy Services will use its electronic accountability system in lieu of sponsor-provided accountability forms.

The detailed procedures to be followed are provided in the Pharmacy Manual.

Study Drug Administration

Each dose of CYT107 will be administered by a registered nurse. CYT107 will be administered by intramuscular route at the dose of 5, 10 or 20 mcg/kg based on the patient's body weight and the dose escalation cohort. (See Body Weight (BW) Calculation above.)

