7.3.2 Within-Dose Safety Monitoring Rule

For each dose $d = 1, 2, 3$, denote $p(d) = \Pr(\text{DLT at dose } d)$. Assume that each $p(d)$ follows a beta(.35, .65) prior. Applying the method of Thall et al.⁴¹, enrollment to dose d will be stopped if $\Pr[p(d) > .35 | \text{data}] > .85$. This criterion will be applied continuously starting at $n = 3$, which implies that accrual to d should be stopped if [number of DLTs] / [number of patients evaluated] is greater than or equal to 3/3 or 4/5. To apply this safety rule for each dose to 2 cohorts of size 3 each may or may not require suspension of accrual. For each dose (a) once 1 or more pats in cohort 1 (pats #1,2,3) have “No toxicity” by day 42 of followup, cohort 2 may begin enrollment, and (b) once 2 or more pats in cohorts 1 and 2 combined (pats #1,2,3,4,5,6) have “No toxicity” by day 42 of follow up, the last patient 7 may be enrolled. This rule has the following operating characteristics.

Operating characteristics of the within-dose safety monitoring rule

True $p(\text{DLT} d)$	$\Pr(\text{Stop accrual to } d)$	Sample Size	Quartiles
.35	.163	7, 7, 7	
.55	.497	4, 7, 7	
.60	.601	4, 6, 7	
.65	.607	3, 4, 7	

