7.4 Enrichment

If enrollment to a dose d is stopped early at $n(d) = 3$ or 6 before 7 patients are treated, then the remaining $7 - n(d) = 1$ or 4 patients will be randomized between the remaining two doses. If enrollment to 2 doses is stopped early, then all remaining patients, up to $N_{\text{max}} = 21$, will be treated at the one remaining dose. If enrollment to all 3 doses is stopped early, then the trial will be stopped with no dose selected.

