7.7 Summary Reports

The investigator is responsible for completing a toxicity summary report and submitting it to the IND Office, Medical Affairs and Safety Group, for review and approval. This should be submitted after the first, the first three, and the first five evaluable patients per cohort, have completed 42 days post-first CYT107 injection.

A copy of the cohort summary should be placed in the Investigator's Regulatory Binder, under "Sponsor Correspondence".

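### Section 7.3.2 lets patient 7 enrol at a dose once 2 of 6 are clear, one patient too few under the plan's own stopping rule while outcomes are pending

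*Combined protocol and SAP*

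**What the plan says.** Section 7.3.2 gives each dose a beta(.35, .65) prior on its DLT probability and closes the dose when Pr(p > .35 | data) exceeds .85. On timing it says "This criterion will be applied continuously starting at" three patients. It prints two boundaries, 3/3 and 4/5. It then says that applying the rule "to 2 cohorts of size 3 each may or may not require suspension of accrual", and sets two conditions per dose:

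- (a) once at least one of patients 1–3 is free of toxicity "by day 42 of followup, cohort 2 may begin enrollment";
- (b) once at least two of patients 1–6 are free of toxicity "by day 42 of follow up, the last patient 7 may be enrolled".

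Section 7.4 deals with a dose whose enrolment "is stopped early at $n(d) = 3$ or 6 before 7 patients are treated".

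Section 4 has a separate pause: "Accrual in between cohorts will be halted for 30 days after the last patient in each cohort has received the last dose of CYT107". It does not refer to Section 7.3.2.

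The word cohort also appears in Section 5.1 ("body weight and the dose escalation cohort") and in Section 7.7, on toxicity summaries: "This should be submitted after the first, the first three, and the first five evaluable patients per cohort". Section 7.1.1 counts DLTs over 42 days from the first injection.

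**The concern.** Conditions (a) and (b) allow accrual to continue without waiting for every outcome. Such a condition is safe if, even when every pending patient goes on to have a DLT, the result is not a stop. Condition (a) passes this test at three patients; condition (b) fails it at six. A team working from Section 7.3.2 alone could dose patient 7 at a level whose first six patients then meet the closing criterion. DLTs here include death and grade 3 or 4 GVHD, so the extra exposure is worth avoiding even though it is one patient.

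Section 4's pause would usually prevent this, but the plan does not say that it applies to the groups of three in Section 7.3.2.

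**Working it through.** **Inputs.** Section 7.3.2: prior beta(.35, .65), target .35, cut-off .85, conditions (a) and (b), and the printed table. Section 7.1.1: 42-day DLT window. Section 4: three weekly doses (days 0, 7, 14) and the 30-day halt.

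**Posterior.** With x DLTs in n patients, p | data ~ beta(.35 + x, .65 + n − x). Pr(p > .35 | data) is:

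| Result | Probability | Decision |
|---|---|---|
| 2/3 | .834 | continue |
| 3/3 | .985 | stop |
| 3/4 | .932 | stop |
| 3/5 | .8485 | continue |
| 4/5 | .973 | stop |
| 3/6 | .746 | continue |
| 4/6 | .929 | stop |
| 4/7 | .865 | crosses |

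In counts, the rule is 3 DLTs at n = 3–4 and 4 DLTs at n = 5–7.

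**The plan's table.** Exact enumeration of six outcomes gives the probability of closing a dose before patient 7:

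| Stops counted | p = .35 | .55 | .60 | .65 |
|---|---|---|---|---|
| 3/3, 4/5 only | .072 | .290 | .372 | .462 |
| plus 3/4, not 4/6 | .127 | .391 | .475 | .563 |
| plus 4/6, not 3/4 | .129 | .457 | .558 | .659 |
| plus both | .165 | .502 | .600 | .694 |
| Plan's table | .163 | .497 | .601 | .607 |

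The first three printed rows are reproduced, to within simulation error, only when both 3/4 and 4/6 count. The .65 row is not reproduced by any of these.

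**Worst case under each condition** (all patients not yet clear go on to a DLT):

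- (a), 1 of 3 clear: 3 − 1 = 2 DLTs, 2/3, .834, not a stop.
- (b), 2 of 6 clear: 6 − 2 = 4 DLTs, 4/6, .929, a stop.
- (b) raised to 3 of 6 clear: 6 − 3 = 3 DLTs, 3/6, .746, not a stop.

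**How often.** Under the full rule, the first crossing is at 4/6 with probability .038, .111, .124 and .131 at p = .35, .55, .60 and .65. The chance of exactly 4/6 without an earlier 3/3, including paths that had already crossed at 3/4, is .076, .222, .249 and .262. This is the ceiling on missed 4/6 stops.

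The actual miss rate depends on accrual, which the documents do not give. Simulation assumed 0.17 to 1 candidate per dose per 30 days, DLT times uniform over 42 days, and the criterion checked on known outcomes. Patient 7 was then dosed ahead of a 4/6 result in roughly .004–.017 of doses at p = .35 and .014–.060 at p = .65. With 3 of 6 required, no 4/6 stop was missed.

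If staff applied only the two printed boundaries, the stops lost at 4/6 would be .129 − .072 = .057 at p = .35 and .659 − .462 = .197 at p = .65.

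**Section 4 halt against the DLT window, for the cohort's last patient:**

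- all three doses on time: 14 + 30 = day 44, past day 42;
- stopped after dose 2: 7 + 30 = day 37;
- stopped after dose 1: 0 + 30 = day 30.

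**Section 7.7.** The summaries come after 1, 3 and 5 patients. The section states no pause and lists no summary at six. A dose at 3/5 (.8485) does not stop at the fifth-patient summary and can still become 4/6.

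**The case against.** Much of the opposing case stands, and it limits the point.

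- **Four observed DLTs would not be ignored.** A reader might infer that the plan enrols patient 7 after seeing 4 DLTs in 6. It does not. Condition (b) is permissive and sits beside a criterion applied continuously, so four known DLTs in six close the dose. The gap exists only while some of the four are pending.
- **The sections do not contradict each other.** A reader might infer that Sections 4 and 7.3.2 conflict. Both can be followed by obeying the stricter. If Section 4's cohorts are the groups of three, its mandatory halt normally lets all six outcomes mature before patient 7. What is missing is a sentence saying so.
- **Cohort is defined for the randomised design.** Section 7.3.2 sets out patients 1–3 and 4–6 within each dose. The narrower point is that Section 4 does not adopt that definition, while Section 5.1 uses the word for a dose group and Section 7.7 for a group of at least five.
- **The printed boundaries may be shorthand.** 3/3 and 4/5 are where the required count changes, so they can be read as including 3/4 and 4/6. Three table rows fit that reading; the unexplained .65 row weakens the table as proof.
- **The early end of the halt is a narrow case.** A patient who stops because of a DLT already has a known outcome, and Section 9 counts withdrawal for toxicity as evaluable and a failure. What remains is a cohort's last patient who stops for another reason (Section 8 allows withdrawal and removal for non-compliance) and then has a late DLT. The documents give no rate for this.

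None of this makes two of six the right threshold: it still fails the worst-case test that condition (a) passes.

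**Conclusion.** Condition (b) is one patient too loose under the plan's own criterion while outcomes are pending (4/6, .929, against a cut-off of .85); condition (a) is correct at the three-patient look. At the planned 7 patients, at most one patient per dose is affected. The posteriors and the ceilings are exact. The miss rates, up to about .06 at p = .65, rest on assumed accrual and DLT timing. Section 4's halt normally closes the gap if its cohorts are those of Section 7.3.2, but the text does not say so, and the halt is not tied to the 42-day window. The severity is minor: this is a threshold correction and a clarification. The documents do not support a claim that the safety rule as a whole fails.

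**What to change.** 1. In Section 7.3.2, raise condition (b) to three or more of six clear at day 42.
2. Print the stops as counts: 3 DLTs at n = 3–4 and 4 DLTs at n = 5–6, noting that 4/7 (.865) also crosses.
3. Keep the Section 4 halt, which is the stricter safeguard. State that it applies to the Section 7.3.2 cohorts within each dose, and that it ends only when every patient in the cohort has completed 42 days from first injection or had a DLT.
4. Recompute the table, including the .65 row, under the rule kept. Decisions at 3 and 6 only give .129/.457/.558/.659. Decisions at 3, 4, 5 and 6 with complete outcomes give .165/.502/.600/.694; in that case Section 7.4 must also provide for closure at 4 or 5.

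A halt between cohorts does not act within patients 4–6, so patients 5 and 6 could still be dosed before a 3/4 result is known. If the sponsor wants that covered, the matching conditions are 2 of 4 clear before patient 5 (worst case 2/4, .694) and 2 of 5 before patient 6 (worst case 3/5, .8485).

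**Cost.** Wording, a short recalculation, no extra patients and somewhat slower accrual within a dose. If Section 4 is already applied to the groups of three, the day-42 ending adds nothing after full on-time dosing (day 44 is later). It adds 42 − 37 = 5 or 42 − 30 = 12 days when the last patient stops after dose 2 or dose 1 without a DLT. Compared with Section 7.3.2 used alone, and under the assumed accrual, raising condition (b) adds about 5 to 10 days on average to fill or close a dose. The full 42-day halt adds about 53 to 63 days at p = .35 and 24 to 30 at p = .65.
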